6.8. Appendix 8: MedDRA PT for Peripheral Edema

The analysis of peripheral edema (Section 4.6.2.1.8) will be based on the TEAEs in the following terms:

- Acute pulmonary oedema
- Ascites
- Brain oedema
- Bronchial oedema
- Capillary leak syndrome
- Cerebral oedema management
- Compression garment application
- Cytotoxic oedema
- Effusion
- Fluid retention
- Gastrointestinal oedema
- Generalised oedema
- Gravitational oedema
- Hydraemia
- Hypervolaemia
- Hypoosmolar state
- Lipoedema
- Lymphoedema
- Negative pressure pulmonary oedema
- Non-cardiogenic pulmonary oedema
- Non-pitting oedema
- Oedema
- Oedema blister
- Oedema due to cardiac disease
- Oedema due to hepatic disease
- Oedema due to renal disease
- Oedema mucosal
- Oedema peripheral
- Pelvic fluid collection
- Pericardial effusion
- Perinephric collection
- Perinephric oedema
- Peripheral swelling
- Pleural effusion
- Pulmonary oedema
- Retroperitoneal effusion
- Retroperitoneal oedema
- Skin oedema
- Skin swelling
- Subdural effusion
- Swelling
- Visceral oedema

6.9. Appendix 9: Empirical Estimation of Relative Event Rate

Traditionally, Poisson distribution has been assumed to draw inference for the rate of rare events. When the event is rare and the sample size is large, it is known that the overall number of events is approximately from Poisson distribution. However, for some not very rare events such as severe hypoglycemic events in T2D patients, the total number of events may not be distributed from Poisson and may be over-dispersed. Assuming Poisson distribution may significantly underestimate the variance, and therefore may reduce the coverage probability and inflate the Type-I error. An empirical method in estimating the variance of the relative event rate without assuming any distribution on the number of events will be provided in this appendix.

Let X_{ij} denote the count response variable for patient j in treatment group i . Let $Y_i = \sum_j X_{ij}$ be the total number of events for treatment group i , and T_i denote the exposure for treatment group i . Let $i = 0$ for the control group and $i = 1$ for the experimental treatment group. The event rate for treatment group i can be calculated as:

$$\hat{r}_i = \frac{Y_i}{T_i}$$

The empirical variance of \hat{r}_i is:

$$\widehat{Var}(\hat{r}_i) = T_i^{-2} \widehat{Var}(Y_i) = T_i^{-2} n_i S_i^2,$$

where S_i^2 is the variance of X_{ij} for treatment group i . Using the delta-method, the variance of $\log(\hat{r}_i)$ can be estimated as:

$$\widehat{Var}(\log(\hat{r}_i)) = Y_i^{-2} n_i S_i^2$$

The relative rate of the experimental treatment versus the control treatment is estimated as:

$$\hat{\lambda} = \frac{\hat{r}_1}{\hat{r}_0}$$

The variances of $\hat{\lambda}$ and $\log(\hat{\lambda})$ are:

$$\widehat{Var}(\hat{\lambda}) = \hat{\lambda}^2 \widehat{Var}(\log(\hat{\lambda}))$$

$$\widehat{Var}(\log(\hat{\lambda})) = \widehat{Var}(\log(\hat{r}_0)) + \widehat{Var}(\log(\hat{r}_1)) = Y_0^{-2} n_0 S_0^2 + Y_1^{-2} n_1 S_1^2$$

Assuming $\log(\hat{\lambda})$ is asymptotically from a normal distribution, the $100(1 - \alpha)\%$ confidence interval for $\log(\hat{\lambda})$ can be constructed as:

$$\left[\log(\hat{\lambda}) - z_{1-\frac{\alpha}{2}} \sqrt{\widehat{Var}(\log(\hat{\lambda}))}, \log(\hat{\lambda}) + z_{1-\frac{\alpha}{2}} \sqrt{\widehat{Var}(\log(\hat{\lambda}))} \right]$$

Then, the $100(1 - \alpha)\%$ confidence interval for $\hat{\lambda}$ is:

$$\left[\hat{\lambda} \exp\left(-z_{1-\frac{\alpha}{2}} \sqrt{\widehat{Var}(\log(\hat{\lambda}))}\right), \hat{\lambda} \exp\left(z_{1-\frac{\alpha}{2}} \sqrt{\widehat{Var}(\log(\hat{\lambda}))}\right) \right] \quad (1)$$

The p-value for testing the null hypothesis of $H_0: \lambda = 1$ is calculated as:

$$p = 2\Phi\left(\left|\log(\hat{\lambda})\right|/\sqrt{Var(\log(\hat{\lambda}))}\right) \quad (2)$$

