For categorical measures, summary statistics will include sample size, frequency, and percentages. Fisher's exact test or logistic regression will be used for treatment comparisons, unless otherwise stated. For laboratory values, both conventional (CN) and System International (SI) units will be presented. Therefore, both % and mmol/mol will be presented for HbA1c and both mg/dL and mmol/L will be presented for glucose measurements.

In this study, the negative binomial regression will be used to analyze the number of hypoglycemic episodes. Group Mean instead of LS mean will be estimated and delta method will be used to estimate the standard error of the Group Mean (Qu and Luo 2015). Group Mean is defined as the mean response in the treatment group for the studied population. The difference between LS mean and the Group Mean is that LS mean estimates the response by taking the

inverse link function on mean covariates, while the Group Mean takes the inverse link function on individual patient covariates first and then averages over all patients. For Level 2 hypoglycemia and severe hypoglycemia, the empirical method based on exposure adjusted rate (calculated by total number of events divided by total exposure) may be used for the treatment comparison if the number of episodes is too small and leads to convergency issues in the negative binomial regression model.

Below table describes the definition of baseline and post-baseline observations for different analyses.

Analysis	Baseline Observations	Post-Baseline Observations
HbA1c (treatment regimen estimand)	The baseline is the last non-missing assessment prior to or at the first day of study treatment.	Planned measurements at Visit 24 (secondary endpoint, Week 26) and Visit 31 (primary endpoint, Week 52) in EAS1. Use unplanned measurements if no planned measurement. Multiple imputation approach will be used to impute missing observations at Visit 24 (Week 26) and Visit 31 (Week 52).
HbA1c (efficacy estimand)	The baseline is the last non-missing assessment prior to or at the first day of study treatment.	Visit 5, 7, 15, 17, 24, 27, and 31 (Weeks 2, 4, 12, 16, 26, 36, and 52) in EAS2 for MMRM. Planned measurements at scheduled visits will be included. Use unplanned measurements if no planned measurements.

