Event rate of Level 2 hypoglycemia events (events/participant/year): • All documented	Baseline, 0-6, 0-12, 0-26, 0-52, 12-26, 26-52 weeks, post-treatment period	Negative binomial regression with treatment and baseline HbA1c as covariates, log (exposure/365.25 days) as the offset in the model. If the number of events is too small to run the negative binomial regression, exposure adjusted rate calculated by total number of events divided by total exposure for individual patients will be provided and the empirical method (see Appendix 9 [Section 6.9] for details) will be used for treatment comparison.
Event rate of Level 3 hypoglycemia events (events/participant/year): • All documented	baseline, 0-26, 0-52, 26-52 weeks, post-treatment period	Negative binomial regression with treatment and baseline HbA1c as covariates, log (exposure/365.25 days) as the offset in the model. If the number of events is too small to run the negative binomial

Endpoint	Analysis Period	Statistical Method
		regression, exposure adjusted rate calculated by total number of events divided by total exposure for individual participants will be provided and the empirical method (see Appendix 9 [Section 6.9] for details) will be used for treatment comparison.
Event rate of Level 2/3 hypoglycemia events (events/participant/year): 
 • All documented • Nocturnal • Non-nocturnal 	baseline, 0-6, 0-12, 0-26, 0-52, 12-26, 26-52 weeks, post-treatment period	Negative binomial regression with treatment and baseline HbA1c as covariates, log (exposure/365.25 days) as the offset in the model. If the number of events is too small to run the negative binomial regression, exposure adjusted rate calculated by total number of events divided by total exposure for individual patients) will be provided and the empirical method (see Appendix 9 [Section 6.9] for details) will be used for treatment comparison. The plots of the mean cumulative functions (MCFs) by each treatment arm will also be created. The population mean for cumulative number of events up to time t, $M(t)$, will be estimated using a nonparametric estimation method described by Nelson (2003).
Incidence of Level 1 hypoglycemia events: 
 • All documented 	Baseline, 0-6, 0-12, 0-26, 0-52, 12-26, 26-52 weeks, post-treatment period	Logistic regression with treatment and baseline HbA1c as covariates.

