Incidence of Level 2 hypoglycemia events: 
 • All documented 	Baseline, 0-6, 0-12, 0-26, 0-52, 12-26, 26-52 weeks, post-treatment period	Logistic regression with treatment and baseline HbA1c as covariates.
Incidence of Level 3 hypoglycemia events: 
 • All documented 	Baseline, 0-26, 0-52, 26-52 weeks, post-treatment period	Logistic regression with treatment and baseline HbA1c as covariates.
Incidence of Level 2/3 hypoglycemia events: 
 • All documented 	Baseline, 0-6, 0-12, 0-26, 0-52, 12-26, 26-52 weeks, post-treatment period	Logistic regression with treatment and baseline HbA1c as covariates.

Endpoint	Analysis Period	Statistical Method

 • Nocturnal • Non-nocturnal 		
Potential persistent-recurrent hypoglycemia events 
 • identified by investigator • identified by pre-specified criteria (defined in Appendix 10 [Section 6.10]) 	Safety analysis period (see definition in Section 4.6)	The number of participants with at least one event will be summarized and compared by Fisher's exact test. The number of events will also be provided. Listings of the events will also be provided.

Abbreviations: HbA1c = hemoglobin A1c; Level 2/3 = Level 2 and Level 3 composite.

Note: The hypoglycemia yearly rate during defined period is calculated by the number of hypoglycemia within the period/number of days patient at risk within the period * 365.25. For rare events, 100-year rate will be provided. The hypoglycemia incidence during defined period indicates if the patient has at least 1 hypoglycemia events within the period (Yes/No).

Note: For treatment group comparison at baseline, baseline HbA1c is not included in the model.

A sensitivity analysis will be done for selected hypoglycemic endpoints where all hypoglycemic events are considered one hypoglycemic event until a succeeding glucose value is ≥ 70 mg/dL.

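### As printed, the SAP's fallback for sparse hypoglycemia rates has a p-value that is never below 1 and no rule for a zero-event arm, and the printed LBGI can never be positive

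*SAP*

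**What the plan says.** **When Appendix 9 applies.** SAP 4.1 allows the empirical method for Level 2 and severe hypoglycemia "if the number of episodes is too small and leads to convergency issues in the negative binomial regression model". The rate table in SAP 4.6.3.1.1 is firmer. For Level 2, Level 3 and Level 2/3 rates it opens the fallback with "If the number of events is too small to run the negative binomial regression" and says that the Appendix 9 method will then make the treatment comparison. SAP 4.6.3.1.2 does the same for the two CGM Level 2 rates.

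**What Appendix 9 prints.** The relative rate λ is the LY3209590 rate divided by the degludec rate. The log-rate variance is "Var}(\log(\hat{r}_i)) = Y_i^{-2} n_i S_i^2", with Y the event count in the arm. Equation (1), the confidence interval, has its lower limit built from "\lambda} \exp\left(-z_{1-\frac{\alpha}{2" and so on. Equation (2), the p-value for λ = 1, is "p = 2\Phi\left(\left|\log(\hat{\lambda})\right|/\sqrt{Var(\log(\hat{\lambda" and so on, with no minus sign and no complement. Nothing is said about Y = 0.

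**Incidence.** SAP 4.1 says that Fisher's "exact test or logistic regression will be used for treatment comparisons, unless otherwise stated". The incidence tables in SAP 4.6.3.1.1 and 4.6.3.1.2 name only logistic regression for the hypoglycemia levels.

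**CGM risk indices.** SAP 6.6.4.1 defines f(BG) = 1.509 × [(ln BG)^1.084 − 5.381]. It sets rl = 10f where f < 0 (otherwise 0) and rh = 10f where f > 0 (otherwise 0). LBGI and HBGI are the means of rl and rh, and BGRI is their sum.

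**The concern.** Each item is a printed rule that gives a wrong answer, or none, if followed literally.

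1. A p-value that is 1 at no difference and rises towards 2 as the arms separate cannot stand beside an interval that excludes 1.
2. The method kept for very few events stops working when one arm has none, which is the sparsest case that it could meet.
3. A low-glucose risk that becomes more negative as glucose falls makes BGRI improve when hypoglycemia is added.

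At stake are the Level 2/3 rate (other secondary), the Level 2 and Level 3 rates (tertiary), the CGM event rates and the within-day variability indices.

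**Working it through.** The SAP gives no worked number for Appendix 9 or for LBGI, so there is no stated figure to reproduce. The formulas were evaluated as printed.

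**1. P-value.** With z = |log λ|/SE ≥ 0:

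| z | printed 2Φ(z) | usual 2[1 − Φ(z)] |
|---|---|---|
| 0 | 1.000 | 1.000 |
| 1 | 1.683 | 0.317 |
| 1.96 | 1.950 | 0.050 |
| 2.576 | 1.990 | 0.010 |

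Example: 888 participants at 1:1 give n = 444 per arm. Assume equal exposure and at most one event per participant, so S² = (Y − Y²/444)/443. For 4 versus 14 events:

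- nS²/Y² = 0.2483 for Y = 4 and 0.0693 for Y = 14. SE = √0.3176 = 0.564.
- λ = 14/4 = 3.5, log λ = 1.253, z = 2.223.
- Equation (1): 3.5 × exp(±1.96 × 0.564) = 1.16 to 10.56, which excludes 1.
- Equation (2) as printed: 1.97. Usual form: 0.026, which agrees with equation (1).

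**2. Zero events.** If Y = 0 in an arm, Y⁻² is undefined. If only the LY3209590 arm is empty, λ = 0 and log λ does not exist. If the degludec arm is empty, λ itself is undefined. Correcting equation (2) does not help.

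How often this could happen depends on event rates, which the documents do not give. Assume Poisson counts, equal rates in both arms and the planned 15% dropout spread evenly. Patient-years per arm are then:

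- 0-52 weeks: 444 × (364/365.25) × 0.925 = 409.3
- 0-26 weeks: 444 × (182/365.25) × 0.9625 = 212.9
- 26-52 weeks: 409.3 − 212.9 = 196.4

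P(at least one zero arm) = 1 − (1 − e^(−rate × PY))²:

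| Assumed Level 3 rate per 100 patient-years | 0-52 weeks | 0-26 weeks | 26-52 weeks |
|---|---|---|---|
| 0.2 | 69% | 88% | 89% |
| 0.5 | 24% | 57% | 61% |
| 1.0 | 3% | 22% | 26% |

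The chance exceeds 5% below 3.68 expected events per arm, which is 0.90 per 100 patient-years over 0-52 weeks. Over-dispersion raises it slightly: gamma-Poisson counts with dispersion 20 give 69.5%, 26.2% and 4.6% over 0-52 weeks, against 68.8%, 24.2% and 3.3% under Poisson.

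**3. LBGI and BGRI.** f is zero at 112.5 mg/dL, f(50) = −1.500, f(150) = +0.537 and f(250) = +1.498.

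| Readings | LBGI | HBGI | BGRI |
|---|---|---|---|
| all at 150 mg/dL | 0 | 5.37 | 5.37 |
| 90% at 150, 10% at 50 | −1.50 | 4.83 | 3.33 |
| 80% at 150, 20% at 50 | −3.00 | 4.30 | 1.30 |
| half at 50, half at 250 | −7.50 | 7.49 | −0.01 |

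As printed, LBGI is never above zero, and adding hypoglycemia lowers the total risk index. The sign of HBGI is not affected.

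**The case against.** **Items 1 and 3 may be reading losses.** The text was machine-read, and one lost mark could explain each. Equation (2) also prints Var without the hat that it carries elsewhere in the appendix. Against that, the minus sign in equation (1), the Y⁻² exponents and the exponent 1.084 all survived, and a lost square would have to be missing from both the rl and the rh line. The available text cannot settle it. A reader might infer that both are proven errors in the approved SAP; that goes further than the evidence.

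**Wrong conclusions are unlikely.** Equation (1) fixes the intended two-sided normal test, and a p-value above 1 would be noticed in output. SAP 6.6.4.1 says that it follows standard formulas from a cited source, which is not available here. Low glucose is also reported directly, as time below 70 and 54 mg/dL and as CGM episodes. All of this stands and limits the harm. The SAP is still the specification against which programs are checked.

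**The zero-event gap is narrow.** Per-arm exposure-adjusted rates are already planned. Severe hypoglycemia also gets a risk-difference summary and a listing (SAP 4.6 and 4.6.2.1.1), and Protocol 9.3.5 allows Fisher's exact test for hypoglycemia incidence. Reporting the ratio as not estimable would be a legitimate convention, but the SAP does not state it, and none of the alternatives compares rates.

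**Zero arms are not a foregone conclusion.** SAP 4.6.3.1.1 lists Level 3 rates for "baseline, 0-26, 0-52, 26-52 weeks, post-treatment period" and adds: "For treatment group comparison at baseline, baseline HbA1c is not included in the model". A reader might infer from the short lead-in, in insulin-naïve participants, that the method is almost bound to fail. In that period it probably would, but a missing pre-treatment comparison bears on no treatment conclusion. For the treatment period the result depends on assumed rates, and Appendix 9 itself describes severe events in type 2 diabetes as not very rare.

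**Conclusion.** The point holds for the text as printed, with limited reach.

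- **Zero events.** This is the firm part and does not depend on PDF reading. The stated fallback gives no interval and no test when an arm has no events, and no other section supplies a rate comparison for that case. The frequency figures rest on assumed Level 3 rates, near-Poisson counts and equal arms.
- **Equation (2).** As printed it cannot give a valid p-value and contradicts equation (1). This is subject to the source PDF.
- **LBGI and BGRI.** As printed, LBGI is zero or negative and BGRI offsets lows against highs. This is also subject to the source PDF.

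The affected analyses are safety and glucose-variability analyses, for which SAP 2.1 makes no multiplicity adjustment. A reader might infer a threat to the trial's main conclusions. There is none: the primary and key secondary tests use neither Appendix 9 nor these indices.

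**What to change.** First check equation (2) and the rl and rh lines against the source PDF and the analysis programs.

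1. If confirmed, replace equation (2) with p = 2[1 − Φ(|log λ|/SE)].
2. Whatever that check shows, add a zero-event rule to Appendix 9. With zero events in one arm, compare the rates by a method that is defined at zero and does not assume Poisson counts, for example a participant-level permutation test of the rate difference. An exact conditional Poisson test fits less well, because Appendix 9 sets the Poisson assumption aside on grounds of over-dispersion. With zero events in both arms, report the per-arm rates without a test.
3. In the incidence tables of SAP 4.6.3.1.1 and 4.6.3.1.2, state that Fisher's exact test replaces logistic regression when an arm has zero events, because the odds ratio then has no finite estimate.
4. If the source PDF confirms the rl line, define rl and rh so that both are non-negative, reconciled with the cited standard formula and the program.

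Cost: up to two corrected formulas, one rule, one clause in two tables and a program check. No new data are needed.

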6.10. Appendix 10: Definition for Persistent-Recurrent Hypoglycemia

[figure not shown]
A P-R hypoglycemia based on programming search in the e-diary database for hypoglycemic events that meet prespecified criteria is defined as a set of hypoglycemic episodes that:

- a) starts with the occurrence of a level 3 or level 2 hypoglycemic episode ($<54\text{mg/dL}$, [3.0 mmol/L]) and is followed by more episodes of hypoglycemia ($<70\text{mg/dL}$, [3.9 mmol/L]), within the day of the initial episode,

AND

b) is followed by at least one episode of hypoglycemia ($<70\text{mg/dL}$, [3.9 mmol/L]) per day, in the next 2 days or longer, and that ends when no hypoglycemia episode occurs for at least 2 days.

An example of a set of hypoglycemic episodes meeting the prespecified criteria for a P-R hypoglycemia event is illustrated in the figure below.

6.11. Appendix 11: Abnormality Level Criteria for Chemistry and Hematology Laboratory Results

Parameter	Level 1	Level 2	Level 3
General Chemistry			
Sodium, low (mEq/L)	<132	<130	<125
Sodium, high (mEq/L)	>150	>155	>160
Potassium, low (mEq/L)	<3.6	<3.4	<3.0
Potassium, high (mEq/L)	>5.5	>6	>6.5
Chloride, low (mEq/L)	<95	<88	<80
Chloride, high (mEq/L)	>108	>112	>115
Bicarbonate, low (mEq/L)	<20	<18	<15
Bicarbonate, high (mEq/L)	N/A	N/A	>30
Blood urea nitrogen, high (mg/dL)	>23	>27	>31
Calcium, low (mg/dL)	<8.4	<8.0	<7.5
Calcium, high (mg/dL)	>10.5	>11.0	>12.0
Phosphate, low (mg/dL)	<2.5	<2.0	<1.4
Protein (total), low (g/dL)	<6.0	<5.4	<5.0
Albumin, low (g/dL)	<3.1	<2.5	<2.0
Uric Acid (urate), high (mg/dL)	>7.0	NA	NA
Kidney Function			
Creatinine, increase (mg/dL)	$\geq 1.5 \times$ baseline	$\geq 2.0 \times$ baseline	$\geq 3.0 \times$ baseline
eGFR, decrease (mL/min/1.73m ²)	$\geq 25\%$ decrease	$\geq 50\%$ decrease	$\geq 75\%$ decrease
Lipids			
Cholesterol (total), high (mg/dL)	>200	>240	>300
HDL, low (mg/dL), males	<40	<30	<20
HDL, low (mg/dL), females	<50	<40	<20
LDL, high (mg/dL)	>130	>160	>190
Triglycerides, high (mg/dL)	>150	>300	>500
Hematology			
Complete Blood Count			
WBC, low (cells/ μ L)	<3500	<3000	<1000
WBC, high (cells/ μ L)	>10,800	>13,000	>15,000
Hemoglobin, decrease (g/dL)	N/A	>1.5 dec. from baseline	>2 dec. from baseline
Hemoglobin, increase (g/dL)	N/A	>2 inc. from baseline	>3 inc. from baseline
Platelets, low (cells/ μ L)	<140,000	<125,000	<100,000
Hemoglobin, low (g/dL), male	12.5-13.5	<12.5	<10.5
Hemoglobin, low (g/dL), female	11.0 – 12.0	<11	<9.5
WBC Differential			
Lymphocytes, low (cells/ μ L)	<1000	<750	<500
Lymphocytes, high (cells/ μ L)	>4000	>10,000	>20,000
Neutrophils, low (cells/ μ L)	<2000	<1000	<500
Eosinophils, high (cells/ μ L)	>650	>1500	>5000

Parameter	Level 1	Level 2	Level 3
Coagulation Studies			
Prothrombin time, increase (sec)	$>1.1 \times \text{ULN}$	$>1.3 \times \text{ULN}$	$>1.5 \times \text{ULN}$

Abbreviations: eGFR = estimated glomerular filtration rate; HDL = high-density lipoprotein; LDL = low-density lipoprotein; WBC = white blood cell.

Note: For liver enzymes, Lilly defined categories will be used.

6.12. Appendix 12: Interaction Effect for Subgroup Analysis – Treatment Regimen Estimand

The ANCOVA analysis will be performed within each subgroup with multiple imputation of missing primary measures. Statistical inference over multiple imputation of missing data will be guided by Rubin (1987) to obtain $\hat{\theta}_1$ and $se(\hat{\theta}_1)$ for the treatment difference in subgroup 1, and $\hat{\theta}_2$ and $se(\hat{\theta}_2)$ in subgroup 2. Then, the distribution of treatment by subgroup interaction (difference of treatment effects) is: $\hat{\theta}_1 - \hat{\theta}_2 \sim N(\theta_1 - \theta_2, [se(\hat{\theta}_1)]^2 + [se(\hat{\theta}_2)]^2)$

A z-statistic can be contrasted such that $z = \frac{\hat{\theta}_1 - \hat{\theta}_2}{\sqrt{[se(\hat{\theta}_1)]^2 + [se(\hat{\theta}_2)]^2}} \sim N(0,1)$, under the null hypothesis of no treatment by subgroup interaction.

For more than 2 groups (k groups),

let $\hat{\theta} = (\hat{\theta}_1, \hat{\theta}_2, \dots, \hat{\theta}_k)$ and $Var(\hat{\theta}) = diag([se(\hat{\theta}_1)]^2, [se(\hat{\theta}_2)]^2, \dots, [se(\hat{\theta}_k)]^2)$.

A chi-square test (df=k-1) can be constructed as

$$T = (C\hat{\theta})'(CVC')^{-1}(C\hat{\theta}) \sim \chi_{k-1}^2$$

where C is a matrix of contrast such that

$$C = \begin{bmatrix} -1 & 1 & 0 & \dots & 0 & 0 \\ 0 & -1 & 1 & \dots & 0 & 0 \\ \dots & \dots & \dots & \dots & \dots & \dots \\ 0 & 0 & 0 & \dots & -1 & 1 \end{bmatrix}$$

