Analysis Model	
After the imputation, the observed and imputed data will be analyzed by the ANCOVA model using treatment, strata (country, GLP-1 RA treatment at randomization, and SU use at randomization), and baseline value of the dependent variable as independent variables. The statistical inference will be based on the multiple imputation framework by Rubin (1987).
	
The MMRM model will include treatment, strata (country, GLP-1 RA treatment at randomization, and SU use at randomization), visit and treatment-by-visit interaction as fixed effects, and baseline of the dependent variable as a covariate. The Kenward-Roger approximation will be used to estimate denominator degrees of freedom for the MMRM models. An unstructured covariance structure will be used to model the within-participant errors. If this structure fails to converge, the following covariance structures will be used in order until one converges:
 
 1. Toeplitz with heterogeneity 2. autoregressive with heterogeneity 3. compound symmetry with heterogeneous variances 4. Toeplitz 5. Autoregressive 6. compound symmetry without heterogeneous variances.

Abbreviation: ANCOVA = analysis of covariance; MMRM = mixed model repeated measurement.

The 2-sided 95% CI of the LS mean difference (LY3209590 – insulin degludec) in the HbA1c change from baseline to Week 52 (Visit 31) will be estimated. For both estimands, LY3209590 will be declared noninferior to insulin degludec if the upper limit of the 2-side 95% CI for the LS mean difference in the HbA1c (measured in %) change from baseline is below NIM of +0.4%. In addition, the 95% CI for the LS mean difference will be compared to an alternative NIM of +0.3%.

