4.7.2. Subgroup analyses

The interaction effects will be evaluated using a significance level of 0.05, unadjusted. Subgroup analyses will be conducted as defined in this section. Additional subgroup analysis may also be performed as appropriate.

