4.7.2.2. Subgroup analyses for HbA1c

Subgroup analyses in HbA1c and change in HbA1c from baseline to Week 52 will be conducted with subgroups defined as (a subgroup category will not be included if there are less than 10 participants in the category):

- Age (<65 years and \geq 65 years),
- Baseline HbA1c stratum (<8.0% and \geq 8.0%),
- Ethnicity,
- Gender,
- Race (white, Asian, American Indian or Alaska Native, Black or African American),
- Region (US and non-US),
- Region (North America, South America, Europe, Asia),
- SU use at randomization,
- Estimated Glomerular Filtration Rate (eGFR) at baseline (<60, 60 - <90, and \geq 90 mL/min/1.73 m²), and
- Duration of diabetes (<median and \geq median).

Analyses for HbA1c and its change will be performed within each subgroup using the same MMRM model for efficacy estimand described for the primary analysis in Section 4.3.2. In addition, the interaction effects will be assessed using the model including the same fixed effects given for the primary analysis model plus factors of subgroup, 2-way interaction of subgroup and treatment, 2-way interaction of subgroup and visit, and 3-way interaction of treatment, visit and the subgroup.

Another subgroup analysis for HbA1c will be conducted for treatment regimen estimand. The ANCOVA analysis for HbA1c for the treatment regimen estimand as described in Section 4.3.2 will be performed within each subgroup. The statistical inference will be based on the multiple imputation framework by Rubin (1987). The p-value for treatment by subgroup interaction will be calculated using a chi-square test based on estimated treatment differences within each subgroup (see details in [Appendix 12](#) [Section 6.12]).

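### The Appendix 12 interaction test has no denominator degrees of freedom, so its nominal 0.05 level becomes about 9–15% if a subgroup category sits at the SAP's 10-participant floor

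*SAP*

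**What the plan says.** SAP 4.7.2 sets the level for all interaction tests: "The interaction effects will be evaluated using a significance level of 0.05, unadjusted".

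SAP 4.7.2.2 lists ten subgroup factors for HbA1c, with one size rule: "a subgroup category will not be included if there are less than 10 participants in the category". A category of exactly 10, both arms together, therefore enters the test. One factor is "Race (white, Asian, American Indian or Alaska Native, Black or African American"). For the treatment regimen estimand the section says: "The p-value for treatment by subgroup interaction will be calculated using a chi-square test based on estimated treatment differences within each subgroup".

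Appendix 12 (SAP 6.12) gives the mechanics: "The ANCOVA analysis will be performed within each subgroup with multiple imputation of missing primary measures". The Rubin estimate and standard error from each category form a z-statistic, referred to N(0,1) "under the null hypothesis of no treatment by subgroup interaction". For k categories a quadratic form in the estimates is used: "A chi-square test (df=k-1) can be constructed as". No denominator degrees of freedom or small-sample correction is given.

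The model fitted within a category is the primary ANCOVA of SAP 4.3.2: treatment, baseline HbA1c and "strata (country, GLP-1 RA treatment at randomization, and SU use at randomization").

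For the efficacy estimand, 4.7.2.2 instead uses a single MMRM with subgroup interaction terms.

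**The concern.** N(0,1) and chi-square references are right when the standard errors are known, and close enough when each rests on many residual degrees of freedom. Near the SAP's floor neither holds. A category of 10 has only a handful of residual degrees of freedom, so its standard error is noisy and often too small. The test can then reject because that category's residual variance came out low by chance, not because the treatment effect differs.

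At stake is the reading of subgroup displays for the estimand intended for the US submission. A race or ethnicity interaction could be flagged at 0.05 on the strength of one very small category.

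**Working it through.** **Inputs from the documents.** Level 0.05 unadjusted (SAP 4.7.2); smallest retained category 10 (SAP 4.7.2.2); ANCOVA terms (SAP 4.3.2); reference distributions (Appendix 12); SD 1.1% (SAP 5), which does not affect the rejection rate when it is common to all categories.

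**Assumptions not in the documents.** One to four countries in the small category; sizes of the other categories; complete data; normal errors with equal SD unless stated.

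**Step 1: reproduce the stated level.** With known standard errors, 2 × (1 − Φ(1.96)) = 0.0500, and the chi-square critical values give 0.0500 for k = 2, 3 and 4. Simulating the planned test with large categories also holds the level:
- 444 v 444: 0.051
- 150/350/388: 0.053
- 250/200/200/238: 0.052

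**Step 2: residual degrees of freedom in a category of 10.** Intercept, treatment, baseline, GLP-1 RA and SU use 5 parameters; c countries add c − 1. Residual df = 10 − 5 − (c − 1), which is 5, 4, 3 and 2 for c = 1, 2, 3 and 4. At c = 6 it is 0 and the model cannot be tested.

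**Step 3: limiting size, one small category against a very large one.** The large category's standard error contributes almost nothing, so the z-statistic behaves as t on the small category's df. True size = 2 × P(t_df > 1.96).

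| Countries | df | Limit | Simulated, 10 v 300 |
|---|---|---|---|
| 1 | 5 | 0.107 | 0.103 |
| 2 | 4 | 0.122 | 0.109 |
| 3 | 3 | 0.145 | 0.141 |
| 4 | 2 | 0.189 | 0.165 |

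Simulations used 8,000 runs per scenario. With larger small categories against 300, the rate was 0.073 at 20, 0.061 at 30 and 0.051 at 50.

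**Step 4: four categories, as for race.** T = (Cθ̂)′(CVC′)⁻¹(Cθ̂) against chi-square(3), with no interaction and sizes 480/150/80/small.

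| Small category | Rejection rate |
|---|---|
| 10 | 9% (1 country), 11% (2), 15% (4) |
| 12 | 7–10% |
| 15 | 7–8% |
| 20 | 6–7% |
| 50 | about 5.5% |

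A different layout, 10/60/300/300 with three countries in the smallest, gave 0.126. Two categories of 10 beside two of 300 gave 0.134 (one country in each small category) and 0.185 (three in each).

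**Step 5: the same data with denominator df.**
- One pooled residual variance and an F test: 0.048–0.052 in five scenarios with at least one category of 10.
- Separate variances with a Satterthwaite t (two categories, 10 v 300): 0.054–0.057.
- Separate variances with a Welch-type F (four categories, one or two of 10): 0.061–0.079. A repeat run with four countries in the small category came nearer 9%.
- Small category's SD 1.3 times the others: the pooled F rejects about 8–9% (up to 11% in one run), and the Welch-type F about 5–6%.

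**The case against.** The strongest case against has four parts.

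- **It bites only near the floor.** This stands. By 20 participants the excess is one to two percentage points, and nothing in the documents shows that any category will be that small.
- **Most of the ten factors are broad splits.** This also stands. With about 888 randomized, age at 65, HbA1c at 8%, gender, SU use, eGFR bands, the region groupings and diabetes duration at the median are not shown to approach 10. A reader might infer that regional interactions, or all ten tests, are at risk; the documents do not support that. Race and possibly ethnicity are the realistic exposure.
- **No confirmatory claim rests on it, and the SAP has a cross-check.** The tests are openly unadjusted. The GLP-1 RA noninferiority tests are analysed separately under SAP 4.4.1.2 and do not use Appendix 12. The efficacy-estimand MMRM would show a discordant result. This limits the consequence, but that MMRM addresses another estimand and does not correct the p-value reported for this one.
- **The obvious replacement has its own weakness.** Appendix 12's separate variances tolerate unequal SDs; a pooled ANCOVA does not. Step 5 confirms this, so the separate-variance option belongs beside it.

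The simulations also omit multiple imputation, so their rates are not the exact level of the planned procedure. The 15% dropout assumption would leave about 8 or 9 observed values in a category of 10 (10 × 0.85 = 8.5), but the net effect after imputation was not computed.

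**Conclusion.** The point holds in a limited form. As written, the Appendix 12 test misses its stated 0.05 level when a category is close to the minimum that the SAP itself sets: about 9–15% with one of four categories at 10, and less as that category grows. Broad splits hold the level.

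A reader might infer that the test generally rejects two to three times too often. That ratio needs a category of almost exactly 10 participants, usually with more than one country in it. The 13–19% result needs two such categories in the same factor. The documents give no category sizes or country counts to establish either.

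The figures rest on complete data and the assumed sizes above. The primary and key secondary tests are unaffected. This is a worthwhile small correction, not a threat to the trial's conclusions.

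**What to change.** Replace the N(0,1) and chi-square references in Appendix 12 with one that carries denominator degrees of freedom. Two options are reasonable:

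1. **One model.** In each imputed data set, fit one ANCOVA on all participants in the retained categories with the primary terms plus subgroup and treatment-by-subgroup. Pool the interaction contrasts by Rubin's rules and use an F reference with small-sample multiple-imputation df. This resembles the SAP's own MMRM interaction model. Its cost is the assumption of common covariate slopes and residual variance, with the unequal-variance penalty shown in Step 5.
2. **Separate fits.** Keep the within-category ANCOVAs and use a Welch/Satterthwaite-type t or F with multiple-imputation df that reflect each category's residual df. This is robust to unequal variances but remains somewhat liberal at 10 participants, at about 5–8% in most scenarios run. Raising the category minimum would reduce that further, at the price of dropping small categories.

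Either needs a short SAP edit and a small program change. No new data are required. The choice should be fixed before unblinding, with category sizes reported beside each interaction p-value.
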